5.2 Recruitment Methods

• State how many subjects will be needed.

About 80 subjects will be recruited and enrolled to meet the enrollment target of 54, out of which it is anticipated 42 will complete the study.

• Describe when, where, how and by whom potential subjects will be identified and recruited.

Recruitment material includes a brochure, flier, and letters to potential participants, clinicians, and service providers. Participants will not be cold called. Researchers will call potential participants only if returning a call or a request to call (e.g., if potential participant left a note requesting phone contact). Recruitment activities will include presentations to individuals and groups associated with PTSD, as well as distribution of approved letters, brochures and flyers. Recruitment activities will target VA clinicians, VA Outpatient Clinics, Veteran Centers, State of California Department of Rehabilitation Veteran Services Programs, Employment Development Department Veterans Outreach programs, County Veterans Services, college programs for veterans, and Travis AFB Transition Service Center, as well as mental health and neurology clinics in local hospitals. Brochures and fliers will be placed in locations approved by the facility being visited, e.g., bulletin boards and brochure display tables. Clinicians on the research team may also provide an-IRB approved brochure or letter to selected patients who may be interested

Step-by-Step Recruitment Process: Research team members will contact or visit the above entities and request permission to leave off brochures, flyers and letters and will also ask if any clinicians or other service staff might be interested in hearing more about the research. If so, researchers will schedule a presentation to clinicians or service providers. Clinicians or service providers may invite potential subjects to these presentations. Brochures, flyers and letters will be available for distribution at presentations. If clinicians or service providers contact the researchers to refer a potential subject, they will be asked to have the subject initiate contact with the research team. If a potential subject expresses interest in person (e.g., at a presentation or if simply observing brochures being distributed), a telephone appointment will be scheduled to discuss the possibility of participation.

Researchers will follow the 'Initial Contact Script' for the first telephone contact with potential subjects. The Informed Consent will be reviewed during this initial telephone contact. If the potential subject continues to express interest and is not clearly ineligible, a telephone screening interview will be scheduled.

If the potential subject continues to express interest by the end of the telephone screening interview, a research clinician or rehabilitation specialist (e.g., neuropsychology fellow, certified rehabilitation counselor) will review the medical record in CPRS. Documents reviewed in the medical record will be those pertinent to eligibility criteria, e.g., diagnosis of PTSD, history of mTBI (not moderate or severe), neurocognitive and psychological testing reports, medication history, current symptoms, evidence of substance abuse, etc. A summary of the medical record review will be provided to the study investigator, who will determine whether the potential subject appears likely eligible and therefore a candidate for the second, in-person screening.

The types of medical records we may review to assess eligibility include: Patient History and Physical Examination, Discharge Summary(ies), X-rays and other Imaging Reports, Diagnostic/Laboratory tests, Drug Abuse Information, Alcoholism or Alcohol Use, Operative Report(s), Progress Notes, and Mental Health (not psychotherapy notes).

If potential subject appears likely to be eligible, the investigator will contact him/her and schedule an appointment for a consent and more in-depth eligibility interview and screen. At this in person meeting, the investigator will go through the informed consent process with the potential subject, including reviewing and signing Form 10-3203 if the subject is agreeable to being videotaped

The above process can be summarized as follows: Screen 1 \rightarrow Medical Record Review \rightarrow Summary to Investigator \rightarrow Investigator determines if Screening 2 to be scheduled \rightarrow Screening 2 (in-person).

A second pathway for Medical Record Review occurs when investigators identify potential subjects through CPRS medical record review or by VA providers providing names of Veterans who may quality (with HIPAA waiver), in which case medical record review takes place before telephone screening. In this case, investigators will assess eligibility of potential subjects through review of medical records in the CPRS database. The subgroup of patients identified as potentially eligible will be sent letters introducing the study to them. The letter will include contact information if they are interested in further information about the study. If the researchers do not hear back from potential subjects within 2 weeks of sending the letter, they will contact the potential subjects once to confirm receipt of letter and ascertain interest.

This second process can be summarized as follows: Identify Potential Subject → Medical Record Review → Send Letter → Follow-up Call (if no hear) → Screen 1 (if interested) → Summary to Investigator → Investigator determines if Screening 2 to be scheduled → Screening 2 (in-person).

 Describe materials that will be used to recruit subjects, e.g., advertisements. Include materials as an appendix or separate attachment.

Recruitment material includes a brochure, flier, and letters to potential participants, clinicians, and service providers.

 Describe any payments to subjects, including the amount, timing (at the end of the study or pro-rated for partial study participation), method (e.g., cash, check, gift card), and whether subjects will experience a delay in receiving the payment. Participants will be paid \$20/hour for the in-person Consent meeting and final screening, \$100 per testing session and \$.55 mile for over 20 miles each way for travel to testing or interventions. If Participants do not participate in any further study activities after the consent/screening meeting, they will be paid by mailed check within 6-8 weeks. If they continue to participate, they will be paid by mailed check within 6-8 weeks of participation in testing sessions. If they decide to withdraw from the study, they will be paid by mailed check in 6-8 weeks after any testing time they already completed before withdrawing.

5.3 Informed Consent Procedures

 Indicate if informed consent will be obtained and/or or if you are requesting a waiver of informed consent or waiver of documentation of informed consent. If the research involves multiple phases, specify for which phases of the research the waiver(s) is being requested and/or the informed consent will be sought.

Informed Consent will be obtained.

 Describe who will be obtaining informed consent, if applicable, and any circumstances that may need to be addressed (e.g. subjects with impaired decision making ability and the use of a legally authorized representative, etc.)

The principal investigator will train all research staff in documenting and obtaining informed consents. No subjects will have impaired decision making ability or require the use of a legally authorized representative.

 If applicable, indicate how local site study personnel will be trained regarding human subjects protections requirements and how to obtain and document informed consent.

The same research staff will be at both sites. All research staff will be trained in obtaining and documenting informed consent.

5.4 Inclusion/Exclusion Criteria

 Describe the criteria that determine who will be included in or excluded from the study.

Inclusion Criteria: Veterans, ages 18 to 75 years, with at least 12 years of education, a current diagnosis of PTSD (DSM IV-R), and a history of mild traumatic brain injury, defined by the American Congress of Rehabilitation Medicine (ACRM) and VA, as a traumatically-induced physiological disruption of brain function as demonstrated by at least one of the following: (1) loss of consciousness of up to 30 minutes; (2) any loss of memory for events immediately before or after the event; (3) any alteration in mental state at the time of the event, for example feeling dazed, disoriented, or confused; and (4) a focal neurological deficit or deficits that may or may not have been transient, for example loss of coordination, speech difficulties, or double vision.

Participants must be in the chronic, stable phase of recovery (>6 months from injury), with residual cognitive difficulties that are affecting daily functioning; on stable psychoactive medications (> 30 days); and able and willing to commit to participate in 10 weeks of training and assessments.

The original inclusion criteria included OIF/OEF/OND Veterans, ages 18 to 55 years, with 12-16 years of education. The protocol was amended to eliminate the OIF/OEF/OND requirement, raise the age limit to 65, and extend the education years. The rationale for these changes were to: 1) expand number of potential subjects to increase likelihood of reaching study enrollment target; 2) increase the eligibility pool to include older veterans with PTSD who may be able to benefit from cognitive interventions, given that PTSD symptoms can last for several years, even decades, after the original trauma; and 3) to expand the eligibility pool to include veterans with more than 4 years of college education, as many veterans have more than 4 years of college.

The amended inclusion criteria included Veterans, aged 18 to 65 years. The protocol was amended to raise the age limit to 75 years. The rationale for this change was to once again expand number of potential subjects to increase likelihood of reaching study enrollment target; 2) increase the eligibility pool to include older veterans with PTSD who may be able to benefit from cognitive interventions, given that PTSD symptoms can last for several years, even decades, after the original trauma.

Exclusion Criteria: A history of moderate or severe TBI (defined by ACRM as having an injury that includes a loss of consciousness lasting longer than 30 minutes, or post-traumatic amnesia lasting longer than 24 hours). Unstable medical, neurologic, or psychiatric condition, including severe cognitive dysfunction, or other reasons for being unable or unwilling to participate in the training and assessments; ongoing illicit drug or alcohol abuse (AUDIT>8); psychosis, severe depression, anxiety or PTSD precluding participation in research activities; current (past 60 days) evidence-based PTSD remediation therapy; poor English comprehension. Eligible participants may have other co-morbid stable neuropsychiatric disorders, including depression. There will be no restriction in regard to gender, race and socioeconomic status.

Inclusion and Exclusion criteria will be verified through the first screening telephone interview (e.g., English speaking ability), medical record review and assessment by the principal investigator during the in-person screening interview.

To ensure that participants' providers (e.g., PCPs and mental health providers) are aware of their participation in a research intervention, we will work with local facilities to flag in CPRS that the patient is enrolled in a cognitive rehabilitation research study. Both the participant and his/her providers will be informed that unless it is medically contra indicated, the participant should stay on the same therapy regiment (particularly with regard to psychoactive medications regiment, or new evidence based behavioral interventions) for the 6 month duration of the study.

5.5 Study Evaluations

 Describe all evaluations to be conducted (including screening; tests/questionnaires that will be administered; any procedures that subjects will be required to complete) and data collection methods. Include materials as an appendix or separate attachment.

Mayo Portland Adaptability Inventory (Malec, et al. 2001), Goal Processing questionnaire; Novakovic-Agopian, Chen, Rome 2007), Profile of Mood States (Lorr and McNear et al., 1988), PCL-M (PTSD Checklist - Military Version), Auditory Consonant Trigrams, Digit Vigilance, Delis-Kaplan Executive Function System (DKEFS), Hopkins Verbal Learning Test - HVLT-R, Brief Visual Memory Test Revised - BVMR-R, Trails A, Trails B, Wechsler Test of Adult Reading-WTAR (Psychological Corporation, 2001), Letter Number Sequencing, WAIS IV, Goal Processing Scale (Novakovic-Agopian, Chen et al 2012), Clinician-Administered PTSD Scale (CAPS- Blake et al, 2000), Beck Depresion Inventory, Difficulties in Emotional Regulation Scale (Gratz and Roemer, 2004). There is also a screening questionnaire.

Mayo Portland Adaptability Inventory does address substance abuse. However, The purpose of the data is to conduct scientific research and that no personnel involved in the study may identify, directly or indirectly, any individual patient or subject in any report of such research or otherwise disclose patient or subject identities in any manner that would suggest the individual patient or subject has been involved or referred to any drug or alcohol treatment program.

The evaluator will videotape the Goal Processing Scale functional assessment if the subject agreed and signed the VA 10-3203 Consent form and continues to agree to being videotaped during the assessment. The subject has the option to refuse this without affecting participation in the study. The video camera will be placed unobtrusively by the subject. Videotaping GPS sessions will allow the evaluator to review the functional assessment later to address any questions or issues related to rating subject performance. Videotaped assessments may be reviewed by other raters to confirm ratings. Videotapes will be stored in locked cabinets in locked VA offices and viewed in locked VA offices.

5.6 Data Analysis

• Provide sample size determination and analysis (include anticipated rate of screen failures, study discontinuations, lost to follow-up etc.).

We estimated sample size requirements for the primary hypotheses for each aim based on the actual preliminary data from veterans who underwent GOALS training. For Attention and Executive Function Overall Domain z score (AVEXE) we found a standardized effect size of 1.2, for the GPS Overall Domain Score (GPSTA) and the Mayo Portland Adaptability Inventory Total Score (MPTST) we found a standardized effect size of 1.1, and for the POMS Total Mood Disturbance Score (POMSTMDZ) we found a standardized effect size of 0.8. Therefore, using the lowest effect size we would estimate that a feasible sample size of 42 patients (21 per group) for each intervention (GOALS and EDU) should yield a power of .80 at an alpha level of 0.05 to detect a standardized effect size of 0.8 or larger.

• Describe how, where and by whom the data will be analyzed.

Tests of repeated measures will be used to assess the effects of the training interventions on pre- and post- intervention measurements. Intervention group x time interactions will be assessed using ANOVA and specific relationships will be tested using paired T-tests.

Practice Effects: Because of repeated testing, improvements on some assessments may be partially due to practice. As a sensitivity analysis, we will compare tests using absolute change scores (as described above) to those using a change index that corrects for practice effects [70]. Specifically, change is operationalized as ((X2-X1)-(M2-M1))/SED, where X1, M1, and X2, M2 are the baseline and follow-up scores for a participant and corresponding group means, respectively; SED is the standard error of the difference. These results will be compared to those obtained from the regression models.

The PI and co-investigators will perform data analysis.

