In a prior study, we assessed the feasibility and effectiveness of GOALS training in individuals with chronic brain injury. Following training, participants showed improvements in accomplishing complex functional tasks in unstructured environment, confirming generalization of training effects to ecologically valid settings. In testing whether functional improvements might be related to improvements in the targeted cognitive functions, we also assessed domain-specific changes utilizing neuropsychological testing. Participants who completed GOALS training also improved on neuropsychological measures of complex attention and executive functions, including working memory, mental flexibility, inhibition and sustained attention. Furthermore, fMRI results after training indicated significantly enhanced modulation of neural processing in extrastriate cortex and changes in prefrontal cortex.

We have been conducting randomized-control study of the effects of GOALS training with Veterans with a history of chronic TBI. Preliminary results indicate improvements on neuropsychological measures of attention and executive function, and performance on complex

real-life tasks. Furthermore, participants had post training improvements on self-report measures reflecting emotional regulation and emotional health. These findings further suggest that improving cognitive control (attentional self-regulation in particular) may also improve functioning in other domains including emotional regulation and complex daily tasks, leading to a novel hypothesis regarding the value of functional improvements in cognition for emotional health.

One of the main goals of any training is to encourage maintenance of benefits even after direct intervention ends. This is of particular practical importance given that therapist time with a patient is always limited. We designed the GOALS intervention to include extensive practice and active application of trained strategies in participants' daily life to maximize the likelihood that the benefits of training would continue beyond the interactions with the trainer. In a follow-up structured interview conducted six months to two years following completion of GOALS training, as many as 92% of participants with chronic brain injury reported that they have integrated and continued to use some of the trained strategies in their daily lives, even in the absence of reinforcements provided by training.

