3.0 Objectives

- Describe the study's purpose, specific aims, or objectives.
- State the hypotheses to be tested.

The overall aim of this proposal is to investigate potential short- and long-term effects of a cognitive training program that targets executive control functions of attentional self- regulation

and goal management, Goal-Oriented Attentional Self-regulation (GOALS), in Veterans with comorbid PTSD - mTBI and cognitive difficulties.

Aim 1: Determination of short and long term effects of cognitive training on neuro-cognitive performance:

Hypothesis 1: Participants who perform GOALS training will demonstrate greater improvements on untrained standardized neuropsychological measures of complex attention and executive function compared to participants who participate in control EDU training.

Hypothesis 2: Improvements in complex attention and executive function will be sustained at six months post GOALS training, suggesting persistence of training benefits.

Aim 2: Determination of short and long term effects of cognitive training on complex real-life functional task performance and daily functioning:

Hypothesis 1: Participants who perform GOALS training will demonstrate greater improvements on untrained complex real-life functional task performance compared to participants who participate in control EDU training.

Hypothesis 2: Participants who perform GOALS training will report greater improvements on self-report measures of daily functioning compared to participants who participate in control EDU training.

Hypothesis 3: Improvements in complex functional task performance and on self-report measures of daily functioning will be sustained at six months post GOALS training, suggesting persistence of training benefits.

Aim 3: Determination of short and long term effects of cognitive training on emotional regulation:

Hypothesis 1: Participants who perform GOALS training will report greater improvements on self-report measures of emotional regulation compared to participants who participate in control EDU training.

Hypothesis 2: Improvements on self-report measures of emotional regulation measures will be sustained at six months post GOALS training, suggesting persistence of training benefits.

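### Section 5.6 does not say whether the planning effect sizes are pre-post GOALS gains or GOALS-minus-EDU differences; if they are pre-post, the stated .80 power is overstated for POMS, the outcome that sets N

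*Combined protocol and SAP*

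**What the plan says.** Section 3.0 of the combined protocol and SAP states the short-term hypotheses as comparisons between arms. Aim 1, Hypothesis 1 predicts "greater improvements on untrained standardized neuropsychological measures of complex attention and executive function compared to participants who participate in control EDU training". Aim 2, Hypotheses 1 and 2, and Aim 3, Hypothesis 1, have the same form.

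Section 5.6 says that the primary hypotheses for each aim were sized "based on the actual preliminary data from veterans who underwent GOALS training". The effects are:

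- AVEXE (attention and executive function): "For Attention and Executive Function Overall Domain z score (AVEXE) we found a standardized effect size of 1.2".
- GPS overall score and Mayo Portland total: 1.1 for both ("the Mayo Portland Adaptability Inventory Total Score (MPTST) we found a standardized effect size of 1.1").
- POMS: "for the POMS Total Mood Disturbance Score (POMSTMDZ) we found a standardized effect size of 0.8".

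The lowest effect is then used for "a feasible sample size of 42 patients (21 per group) for each intervention (GOALS and EDU"), with power .80 at alpha 0.05 for an effect of 0.8 or larger. The paragraph does not state the contrast behind the effects, the SD used to standardise them, or whether the test is one- or two-sided. The planned analysis is a group-by-time interaction in ANOVA, followed by paired t-tests.

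Under practice effects, the same section says that "improvements on some assessments may be partially due to practice". The Interventions section of the 2019 protocol abstract describes EDU as an active comparison matched to GOALS for therapist time, homework and group participation. Section 2.0 mentions one source of veteran data: "We have been conducting randomized-control study of the effects of GOALS training with Veterans with a history of chronic TBI". It reports those results as improvements and gives no difference between arms.

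**The concern.** The sample size calculation uses 0.8 as the GOALS-minus-EDU difference, because it divides 42 people into two groups of 21. The sentence that introduces the effects describes people who received GOALS, and the most natural reading of that is a gain from before to after training. These are different quantities. A pre-post gain contains the specific effect of GOALS plus whatever comes from retesting, therapist contact, group membership and time. EDU was designed to match much of that, so the between-arm difference keeps only what EDU does not share.

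The stake is greatest for POMS. If its planning effect includes shared gain, the trial has clearly less than .80 power for Aim 3, and a non-significant POMS result could not be read as absence of benefit.

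**Working it through.** **Inputs.** From section 5.6: n = 21 per group, alpha 0.05, and planning effects of 0.8 (POMS), 1.1 (GPS, Mayo Portland) and 1.2 (AVEXE). Assumed, because the documents give no figure: a gain g of 0 to 0.3 SD that EDU shares. All effects are taken to be in units of the SD of change.

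**Test.** With two occasions (baseline and week 5) and two groups, the interaction F test on 1 and 40 degrees of freedom is the square of the two-sample t-test on change scores. The planned analysis is therefore equivalent to a two-sided test. One-sided figures are also shown because the plan does not state sidedness.

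**Formula.** Net difference d = planning effect − g. Under a noncentral t with 40 degrees of freedom, the noncentrality is d × √(n/2) = d × √10.5 = 3.240d. The critical values are 2.021 two-sided and 1.684 one-sided.

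**The plan's own figure.** At d = 0.8 the noncentrality is 3.240 × 0.8 = 2.592. Power is .817 one-sided and .716 two-sided. The stated .80 therefore reproduces only as a one-sided two-group comparison, for which 21 per group is exactly the required size. Two-sided, .80 needs 26 per group. As a paired test in 21 people, power would be .936, so the plan did not size a within-arm test.

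**Power if the effects are pre-post and EDU shares g (two-sided / one-sided).**

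| Shared g | POMS (0.8 − g) | GPS, Mayo Portland (1.1 − g) | AVEXE (1.2 − g) |
|---|---|---|---|
| 0 | .716 / .817 | .935 / .968 | .967 / .985 |
| 0.1 | .600 / .721 | .885 / .938 | .935 / .968 |
| 0.2 | .475 / .605 | .812 / .889 | .885 / .938 |
| 0.3 | .353 / .479 | .716 / .817 | .812 / .889 |

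**Detectable difference.** With 21 per group, .80 power requires a net difference of 0.886 two-sided or 0.781 one-sided.

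**Sensitivity to the standardiser.** If 0.8 is in baseline SD units, the effect on the change scale is 0.8 / √(2(1 − r)), where r is the pre-post correlation (assumed). Two-sided power for POMS:

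| r | No shared gain | Shared 0.3 baseline SD |
|---|---|---|
| 0.3 | .571 | .267 |
| 0.5 | .716 | .353 |
| 0.7 | .904 | .532 |

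The unstated standardiser can therefore move power in either direction. In all three cases a shared gain of 0.3 takes it well below .80.

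**The case against.** The strongest reply is that the documents never say the effects are pre-post. Section 2.0 mentions a randomised study in veterans, which could have supplied a between-arm contrast. This stands, and it makes the point conditional. A reader might infer that no comparator change was subtracted. The text is silent on that, although its wording leans that way.

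A reader might also infer that the .80 does not apply to the hypotheses at all. That goes too far. The statement is conditional on an effect of 0.8 or larger, and for a one-sided two-group test it is correct. What lacks support is treating 0.8 as a plausible GOALS-minus-EDU difference.

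Nor can 0.8 be called an upper bound on the net effect. That would require the effects to be pre-post, EDU not to worsen, and the standardiser to be the SD of change. None of these is stated.

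It can be said that the fall from .80 to .72 concerns sidedness and not shared gain. That is right, and only the fall below .72 two-sided, or below .82 one-sided, belongs to shared gain. The two-sided column is still the relevant one, because it matches the planned F test. One-sided, a shared 0.1 already takes POMS to .72.

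The practice remark covers only some assessments. POMS is a self-report mood score, for which non-specific benefit is a likelier source of shared gain than test practice (my judgement). GPS has three alternate forms to control practice, according to the 2019 abstract. Both facts limit the practice argument. Neither removes gain shared through contact and group participation.

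Finally, Progress to date in the 2019 abstract reports significant week-5 improvement after GOALS but not after EDU, from 40 completers. This postdates the sizing and gives no between-arm estimate, and a non-significant change in one arm does not show zero change. It bears on how large the shared gain might be but does not settle it.

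**Conclusion.** The point holds in conditional form. Section 5.6 applies effects attributed to GOALS recipients to between-arm hypotheses without stating the contrast. If they are pre-post gains, the stated .80 is overstated for POMS: a shared gain of 0.1, 0.2 or 0.3 SD gives two-sided power of .60, .475 or .35 (one-sided .72, .605 or .48). These figures assume 21 completers per group, effects in SD-of-change units, and a shared gain that the documents do not quantify.

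A reader might infer that the whole trial is underpowered. The documents do not support that. With a shared 0.3, two-sided power is still .81 for AVEXE and .72 for GPS and Mayo Portland (one-sided .89 and .82). The exposure lies mainly with the outcome that sets N. If the effects were between-arm and expressed in SD-of-change units, the shared-gain issue disappears and only the sidedness question (.72 against .82) remains.

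**What to change.** Revise the sample size paragraph in section 5.6 as follows:

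1. State whether 1.2, 1.1 and 0.8 are pre-post or between-arm effects, which SD standardises them, and whether the test is one- or two-sided.
2. Name the source population. The only veteran GOALS data described (section 2.0) are in chronic TBI, and the documents do not link them explicitly to the sizing.
3. If the randomised study in section 2.0 can supply a between-arm difference in change, and its comparator resembles EDU, use that difference divided by the SD of change.
4. Otherwise, replace the .80 claim with power at net differences of 0.5 to 0.8. State that 21 per group gives .80 power for net differences of about 0.89 SD of change or larger (two-sided).

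The cost is one reworded paragraph, plus a between-arm summary if the data exist. Enrolment does not change; the 2019 abstract reports it closed. The stated power may become less favourable. In return, a non-significant POMS result would be read against the power the trial actually has.

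### The stated .80 power at 21 per group fits a one-sided test the plan never declares; the named group-by-time ANOVA gives about .72 if 0.8 is a between-group effect in change-score SD units, and the plan does not define the 0.8

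*Combined protocol and SAP*

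**What the plan says.** All the relevant text is in section 5.6 (Data Analysis) of the combined protocol and SAP, unless noted.

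- **Size and power.** The plan takes "a feasible sample size of 42 patients (21 per group) for each intervention (GOALS and EDU") and says this "should yield a power of .80 at an alpha level of 0.05 to detect a standardized effect size of 0.8 or larger". Section 5.2 enrols 54 and expects 42 to complete, so 21 per group is the completer count.
- **Source of the effect.** The effect sizes are "based on the actual preliminary data from veterans who underwent GOALS training". They are 1.2 for the attention and executive function score, 1.1 for the GPS and for the Mayo Portland total, and, for the outcome that sets the sample size, "for the POMS Total Mood Disturbance Score (POMSTMDZ) we found a standardized effect size of 0.8".
- **Test.** Repeated-measures tests are used "to assess the effects of the training interventions on pre- and post- intervention measurements", and "Intervention group x time interactions will be assessed using ANOVA and specific relationships will be tested using paired T-tests".
- **Other models.** After the practice-effect sensitivity analysis the section adds: "These results will be compared to those obtained from the regression models". No regression model is specified.

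Neither document states whether the test is one- or two-sided, which contrast the effect sizes describe, which SD they are divided by, or a pre-post correlation.

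**The concern.** A power figure belongs to a particular test and a particular definition of the effect. Here the test is named, but the effect is not defined, and the stated .80 is not what the named test delivers when 0.8 is used directly as the between-group effect. An ANOVA interaction with one degree of freedom is two-sided by construction. The hypotheses in section 3.0 are worded directionally, but that does not declare a one-sided test.

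The stake is the reading of a null result for Aim 3 (emotional regulation), whose POMS effect of 0.8 sets the sample size. The plan implies a 20% risk of missing that effect at the planned size. For the named test the risk is about 28% on the change-score reading, and from 43% to 10% on the raw-SD reading (assumed correlation 0.3 to 0.7).

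The undefined contrast may matter more widely. If the preliminary effects are pre-post gains in GOALS participants, they include any gain that EDU participants would also show, and section 5.6 itself accepts that "improvements on some assessments may be partially due to practice". In that case power for the 1.1 and 1.2 outcomes is lower too.

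**Working it through.** **Inputs from section 5.6:** n = 21 per group, alpha = 0.05, d = 0.8, stated power .80. Every correlation and every non-specific share below is an assumption, because the documents give none.

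**Number of time points.** Section 5.1 gives GOALS to the EDU arm after week 5, so GOALS can be compared with EDU alone only from baseline to week 5. With two groups and two time points, the interaction F test has 1 and 40 df and equals the two-sided t test on change scores.

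**1. Reproducing the plan's figure.** For a two-sample t test, df = 2n − 2 = 40 and the noncentrality is d × √(n/2) = 0.8 × √10.5 = 2.592.

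| n per group | one-sided 0.05 | two-sided 0.05 |
|---|---|---|
| 20 | 0.799 | 0.693 |
| 21 | **0.817** | **0.716** |
| 25 | 0.874 | 0.791 |
| 26 | 0.885 | 0.807 |

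The smallest n reaching .80 is 21 one-sided and 26 two-sided. The noncentral F with 1 and 40 df and noncentrality 0.8² × 21/2 = 6.72 gives the same 0.716. A two-sided paired t test within one arm (n = 21, noncentrality 0.8 × √21) gives 0.936, so that does not explain .80 either.

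**2. The named test, with effects in change-score SD units.** Two-sided power at 21 per group is 0.716 at 0.8, 0.935 at 1.1 and 0.967 at 1.2. The effect detectable with .80 power is 0.886 (0.781 one-sided).

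**3. If 0.8 is in raw-score SD units.** With pre-post correlation ρ, the effect on the change-score scale is d/√(2(1 − ρ)).

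| assumed ρ | effect on change scale | two-sided power at 0.8 |
|---|---|---|
| 0.3 | 0.676 | 0.571 |
| 0.5 | 0.800 | 0.716 |
| 0.6 | 0.894 | 0.807 |
| 0.7 | 1.033 | 0.904 |

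Power equals .80 at ρ ≈ 0.59. At ρ = 0.3, power is 0.836 at 1.1 and 0.894 at 1.2.

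If the analysis adjusts for baseline instead, the effect is d/√(1 − ρ²) with 39 df. Power at 0.8 is then 0.755, 0.788 and 0.831 for ρ = 0.3, 0.4 and 0.5, and equals .80 at ρ ≈ 0.43.

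**4. If the effects are gains within GOALS participants.** Suppose a share f of each gain is non-specific and also occurs under EDU. The between-group effect is then d(1 − f), taken here in change-score SD units.

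| assumed f | power at 0.8 | at 1.1 | at 1.2 |
|---|---|---|---|
| 0 | 0.716 | 0.935 | 0.967 |
| 0.2 | 0.526 | 0.795 | 0.859 |
| 0.3 | 0.425 | 0.683 | 0.757 |

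Power falls below .80 once f exceeds 1 − 0.886/1.1 = 0.19 for the 1.1 outcomes, or 1 − 0.886/1.2 = 0.26 for the 1.2 outcome.

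**The case against.** **The one-sided match is an inference.** A raw-SD effect with ρ = 0.6 gives 0.807 two-sided, closer to .80 than the one-sided 0.817. Each route needs one unstated input. This stands: the match does not show how the .80 was obtained. It does not rescue the figure, because either the power is overstated for the named test or it rests on an input the reader cannot see.

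**The .72 is one reading among several.** This is also true. The Introduction (section 2.0) mentions an ongoing randomized study of GOALS with preliminary results, so a between-group effect may have been available, but the text does not say which contrast was used. The .72 has to stay conditional.

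**More were enrolled than planned.** The Protocol's Progress to date section reports 76 enrolled. At the plan's 42/54 completion rate that would be 76 × 42/54 ≈ 59 completers, with two-sided power of about 0.855 at 0.8. If the 76 correspond instead to the roughly 80 in section 5.2, completers would be 76 × 42/80 ≈ 40, with power of about 0.69. No final completer count is given, so achieved power cannot be derived. The finding therefore concerns the planned size, and the risks quoted apply to that size.

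**Training is delivered in groups.** The Protocol's Interventions section describes groups of 2 to 5, and the calculations here treat participants as independent. Positive correlation within groups would lower every between-arm figure, so this does not favour the stated .80.

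**Nothing in the data changes.** Enrolment is closed and analysis has started. That limits the remedy to wording, but the stated power still frames how a null result is read.

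**Conclusion.** The concern holds. For the named two-sided group-by-time test at 21 per group, power at 0.8 is about 72% rather than 80%, provided that 0.8 is a between-group effect in change-score SD units, the comparison runs from baseline to week 5, and participants are independent. On that reading the shortfall is about 8 percentage points and is confined to the POMS outcome; power at 1.1 and 1.2 is 94% and 97%.

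The stated .80 can be supported only by something the plan leaves out: a one-sided test, or raw-SD units with a correlation of about 0.59 (about 0.43 with baseline adjustment). If the preliminary effects are within-arm gains, power for the other outcomes may also fall below .80. The arithmetic is firm. Which reading the authors intended cannot be settled from the documents.

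**What to change.** In section 5.6:

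1. Define the effect sizes 1.2, 1.1, 1.1 and 0.8: say whether each is a pre-post gain in GOALS participants or a GOALS-minus-EDU difference, and which SD it is divided by.
2. Restate power for the planned two-sided test accordingly:
   - Between-group effect in change-score SD units: about 72% power at 0.8 (two-sided alpha 0.05), detectable effect 0.89 at 80% power, about 94% at 1.1 and 97% at 1.2, taking participants as independent.
   - Raw-score SD units: state the pre-post correlation and the power it gives.
   - Within-arm gain: state the gain assumed under EDU and give power for the difference.
3. If .80 is kept, state the sidedness, model and correlation that support it. If it came from a one-sided calculation, say so.

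The cost is a few sentences. No test, estimate or participant changes, and no extra enrolment is needed. On the change-score reading the stated power becomes less favourable.
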